**Table 1. Identity of Investigational Product**

| Study Drug             | Dosage Form   | Strength   | Route of Administration | Manufacturer |
|------------------------|---|--|-------------------------|--------------|
| ABBV-3373              | Lyophilized powder for solution for infusion in vials | 50 mg/mL when reconstituted with 1.2 mL of sterile water for injection; 1 mL extractable volume per vial; further dilution into saline for IV infusion | IV                      | AbbVie       |
| Placebo for ABBV-3373  | Lyophilized powder for solution for infusion in vials | N/A  | IV                      | AbbVie       |
| Adalimumab             | Pre-filled syringe                                    | 80 mg/0.8 mL   | SC                      | AbbVie       |
| Placebo for Adalimumab | Pre-filled syringe                                    | N/A  | SC                      | AbbVie       |

IV = intravenous; N/A = not applicable; SC = subcutaneous

## 5.8 Randomization/Drug Assignment

All subjects will be assigned a unique identification number by the IRT at the screening visit. For subjects who rescreen, the screening number assigned by the IRT at the initial screening visit should be used. The IRT will assign a randomization number that will encode the subject's treatment group assignment according to the randomization schedule generated by the statistics department at AbbVie.

Randomization will be stratified by factors listed in Section 4.1.

Forty-five subjects will be randomized to either the ABBV-3373 or adalimumab control arm according to a 2:1 ratio. Randomization will be stratified by the following factors:

- Stratification by current use of systemic GC ( $\leq 7.5$  mg/d prednisone equivalent) for treatment of RA at BL (yes/no).
- Stratification by prior exposure to non-anti-TNF biologics or targeted synthetic DMARDs (< 3 months and terminated not due to lack of efficacy or intolerance) (yes/no).

All AbbVie personnel with direct oversight of the conduct and management of the trial (with the exception of AbbVie Drug Supply Management Team), the investigator, study site personnel, and the subject will remain blinded to each subject's treatment throughout the study. To maintain the blind, the ABBV-3373 vials and matching placebo vials, as well as adalimumab PFS and matching placebo PFS, will be provided for the study. The IRT will provide access to unblinded subject treatment information in the case of a medical emergency. The procedure for breaking the blind is referenced in the IRT Training Slides provided to each study site.

AbbVie must be notified before the blind is broken unless identification of the study drug is required for medical emergency, i.e., situation in which the knowledge of the specific blinded treatment will affect the immediate management of the subject/patient's conditions (e.g., antidote is available). AbbVie must then be notified within 24 hours of the blind being broken. See [Appendix K](#) for contact information, including 24/7 AbbVie emergency contact coverage.

## 5.9 Protocol Deviations

---

The investigator is responsible for complying with all protocol requirements, written instructions, and applicable laws regarding protocol deviations. Protocol deviations are prohibited except when necessary to eliminate an immediate hazard to study subjects. If a protocol deviation occurs (or is identified), the investigator is responsible for notifying IEC/independent review board (IRB), regulatory authorities (as applicable), and AbbVie.

## 6 SAFETY CONSIDERATIONS

### 6.1 Complaints and Adverse Events

---

#### Complaints

A complaint is any written, electronic, or oral communication that alleges deficiencies related to the physical characteristics, identity, quality, purity, potency, durability, reliability, safety, effectiveness, or performance of a product/device. Complaints associated with any component of this investigational product must be reported to AbbVie.

#### Product Complaint

A product complaint is any complaint related to the biologic or drug component of the product or to the medical device component(s).

For a product this may include, but is not limited to, damaged/broken product or packaging, product appearance whose color/markings do not match the labeling, labeling discrepancies/inadequacies in the labeling/instructions (e.g., printing illegible), missing components/product, device not working properly, or packaging issues.

Product complaints concerning the investigational product and/or device must be reported to AbbVie within 1 business day of the study site's knowledge of the event. Product complaints occurring during the study will be followed up to a satisfactory conclusion.

#### Medical Complaints/Adverse Events and Serious Adverse Events

An AE is defined as any untoward medical occurrence in a subject or clinical investigation subject administered a pharmaceutical product and which does not necessarily have a causal relationship with this treatment. An AE can therefore be any unfavorable and unintended sign (including an abnormal laboratory finding), symptom, or disease temporally associated with the use of a medicinal (investigational) product, whether or not the event is considered causally related to the use of the product.

The investigators will monitor each subject for clinical and laboratory evidence of AEs on a routine basis throughout the study. All AEs will be followed to a satisfactory conclusion.

An elective surgery/procedure scheduled to occur during a study will not be considered an AE if the surgery/procedure is being performed for a pre-existing condition and the surgery/procedure has been pre planned prior to study entry. However, if the pre-existing condition deteriorates unexpectedly during the study (e.g., surgery performed earlier than planned), then the deterioration of the condition for which the elective surgery/procedure is being done will be considered an AE.

If any of the following SAEs or AEs are reported, then the following supplemental report must be completed.

| Serious Adverse Event   | Supplemental Report |
|---|---------------------|
| Cardiac events
Myocardial infarction or unstable angina
Heart failure
Cerebral vascular accident and transient ischemic attack
Cardiovascular procedures (SAE Supplemental Procedure eCRF) | MACE eCRF           |
| Discontinuation or interruption of study drug due to a hepatic-related AE
A hepatic-related SAE
ALT/AST > 8 × ULN or ALT/AST > 3 × ULN with a total bilirubin > 2 × ULN                               | Hepatic AE eCRF     |

AE = adverse event; ALT = alanine aminotransferase; AST = aspartate aminotransferase; eCRF = electronic Case Report Form; MACE = major adverse cardiac event; SAE = serious adverse event; ULN = upper limit of normal

If an AE, whether associated with study drug or not, meets any of the following criteria, it is to be reported to AbbVie clinical pharmacovigilance or contract research organization (as appropriate) as a SAE within 24 hours of the site being made aware of the SAE (refer to Section 4.3 of the Operations Manual for reporting details and contact information):

|   |  |
|---|--|
| Death of Subject                                   | An event that results in the death of a subject.   |
| Life-Threatening                                   | An event that, in the opinion of the investigator, would have resulted in immediate fatality if medical intervention had not been taken. This does not include an event that would have been fatal if it had occurred in a more severe form. |
| Hospitalization or Prolongation of Hospitalization | An event that results in an admission to the hospital for any length of time or prolongs the subject's hospital stay. This does not include an emergency room visit or admission to an outpatient facility.                                  |
| Congenital Anomaly                                 | An anomaly detected at or after birth, or any anomaly that results in fetal loss.  |

|  |  |
|--|--|
| Persistent or Significant Disability/Incapacity   | An event that results in a condition that substantially interferes with the activities of daily living of a study subject. Disability is not intended to include experiences of relatively minor medical significance such as headache, nausea, vomiting, diarrhea, influenza, and accidental trauma (e.g., sprained ankle).   |
| Important Medical Event Requiring Medical or Surgical Intervention to Prevent Serious Outcome | An important medical event that may not be immediately life-threatening or result in death or hospitalization, but based on medical judgment may jeopardize the subject and may require medical or surgical intervention to prevent any of the outcomes listed above (i.e., death of subject, life threatening, hospitalization, prolongation of hospitalization, congenital anomaly, or persistent or significant disability/incapacity). Additionally, any elective or spontaneous abortion or stillbirth is considered an important medical event. Examples of such events include allergic bronchospasm requiring intensive treatment in an emergency room or at home, blood dyscrasias or convulsions that do not result in inpatient hospitalization, or the development of drug dependency or drug abuse. |

All adverse events reported from the time of study drug administration until 70 days after discontinuation of study drug administration will be collected, whether solicited or spontaneously reported by the subject. In addition, serious adverse events and protocol-related nonserious adverse events will be collected from the time the subject signs the study-specific informed consent.

AbbVie will be responsible for Suspected Unexpected Serious Adverse Reactions (SUSAR) reporting for the Investigational Medicinal Product (IMP) in accordance with global and local requirements.

Adverse events will be monitored throughout the study to identify any of special interest that may indicate a trend or risk to subjects.

### Serious Adverse Event Reporting

AbbVie is committed to continue to collect safety information including those events that may occur in this trial in order to confirm this established safety profile and to identify any unknown potential adverse reactions, rare events, and those events with a long latency. AbbVie is participating in a Food and Drug Administration-requested, TNF inhibitor class wide exploration of the rare appearance of malignancy in subjects/patients who are 30 years of age or younger at the time of diagnosis. The risk of malignancy in this age group has not been established and is difficult to study due to its rarity. AbbVie appreciates your attention to the additional reporting requirements needed in this unlikely event. In the event of an SAE, and additionally, any nonserious event of malignancy in subjects 30 years of age and younger, whether related to SC study drug or not, the physician will notify Clinical Pharmacovigilance within 24 hours of the physician becoming aware of the event by entering the SAE or nonserious event of malignancy in subjects 30 years of age and younger data into the electronic data capture (EDC) system. Serious adverse events and nonserious events of malignancy in subjects 30 years of age and younger, that occur prior to the site having access to the RAVE® EDC system or if RAVE® is not operable, should be documented on the SAE non-case report form forms and emailed (preferred route) or faxed to the Clinical Pharmacovigilance within 24 hours of being made aware of the SAE.

## Adverse Events of Special Interest

The following adverse events of special interest will be monitored during the study:

- Serious infections, opportunistic infections, herpes zoster, and TB;
- Malignancy (all types);
- Cardiovascular events (e.g., major adverse cardiovascular event [MACE]);
- Hematologic disorders (i.e., anemia, neutropenia, lymphopenia);
- Hepatic disorders;
- Hypersensitivity reactions, including all serious allergic reactions;
- Demyelinating disease;
- Systemic GC side effects (i.e., infections, skin atrophy, weight gain, cataract, hypertension, indigestion, hyperglycemia).

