#### Why Is This Study Being Conducted

Tumor necrosis factor (TNF) $\alpha$  antagonists reduce the signs and symptoms of disease by reducing inflammation and limiting the progression of tissue destruction and are considered effective therapies with established safety profiles in patients with immune-mediated inflammatory diseases, including rheumatoid arthritis (RA). Nevertheless, TNF $\alpha$  antagonists as well as other biologics and targeted synthetic disease-modifying antirheumatic drugs (DMARDs) provide 50% improvement in arthritis scores (American College of Rheumatology 50% improvement criteria [ACR50]) for fewer than half of RA subjects, even in combination with methotrexate (MTX), indicating that there remains an unmet clinical need for improved therapies.

Glucocorticoid receptor modulators (GRMs) are potent drugs for treating many inflammatory diseases. In RA, GRMs such as prednisone are highly effective at reducing inflammation and fatigue as well as relieving pain. However, the administration of GRMs is limited due to their side effect profile including (but not limited to) hypothalamic-pituitary-adrenal (HPA) axis suppression, increased rates of bone fracture due to osteoporosis, hyperglycemia, glaucoma, skin thinning and weight gain. Thus, the full efficacy of GRM therapy is not achieved with existing agents due to systemic side effects.

ABBV-3373 is an antibody-drug conjugate (ADC) composed of adalimumab (the active component of Humira®) conjugated to A-1677770, a proprietary, highly potent GRM (also referred to as the payload) being developed for the treatment of immune-mediated inflammatory diseases including RA. This adalimumab/GRM ADC has the potential to deliver a highly potent anti-inflammatory payload selectively to the activated immune cells that express transmembrane TNF, and meanwhile to minimize systemic exposure to the free payload GRM. Therefore, the adalimumab/GRM ADC is promising as a novel therapeutic agent which can achieve transformational efficacy relative to adalimumab while reducing side effects caused by free GRM systemic exposure.

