### Management of GC-Induced Adrenal Insufficiency

High dose or long term use of corticosteroids can produce reversible HPA axis suppression with the potential for GC insufficiency after withdrawal of treatment. Drug-induced secondary adrenocortical insufficiency may be minimized by gradual reduction of dosage. This type of relative insufficiency may persist for months after discontinuation of therapy; therefore, hormone therapy should be reinstated in any situation of stress occurring during that period.

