## 7.4 Statistical Analyses for Safety

---

Safety analyses will be carried out using the Safety Analysis Set. There will be 2 sets of planned safety analyses: safety analysis by Week 12 and long-term safety analysis. Safety will be assessed by AEs, laboratory assessments, and vital signs. Frequency tables of subjects with treatment emergent AEs by preferred term (PT), by system organ class (SOC) and PT as in the Medical Dictionary for Regulatory Activities, by severity, and by relationship to the study drug as assessed by the Investigator will be provided.

Summaries of SAEs, deaths, AEs leading to discontinuation, and Areas of Safety Interest will be provided as well. The changes from BL in clinical laboratory and vital sign values by visit will be analyzed in a descriptive manner. Shift of selected laboratory values from BL to defined time points will be tabulated. The number and percentage of subjects meeting the criteria for potentially clinically significant laboratory/vital sign/ physical examination/ECG values will be summarized.

No external data borrowing will be applied for safety analyses.

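### The closed list of systemic glucocorticoid (GC) effects of special interest in Section 6.1 leaves out adrenal insufficiency, osteoporotic fracture and glaucoma, so the grouped summary would not count them

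*Protocol*

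**What the plan says.** Section 6.1 (Adverse Events of Special Interest) lists eight categories to be monitored. The last is "Systemic GC side effects (i.e., infections, skin atrophy, weight gain, cataract, hypertension, indigestion, hyperglycemia". The cardiovascular category in the same list is worded differently, as an open example: "Cardiovascular events (e.g., major adverse cardiovascular event [MACE".

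Section 2.1 sets out why existing GRMs cannot be used to full effect. It says that "the administration of GRMs is limited due to their side effect profile including (but not limited to) hypothalamic-pituitary-adrenal (HPA) axis suppression", and continues with "increased rates of bone fracture due to osteoporosis, hyperglycemia, glaucoma, skin thinning and weight gain".

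Section 6.2 has a separate paragraph on GC-induced adrenal insufficiency, which states: "High dose or long term use of corticosteroids can produce reversible HPA axis suppression with the potential for GC insufficiency after withdrawal of treatment".

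Section 3.4 names AESIs within the first safety endpoint. Section 7.4 says how such events will be reported: "Summaries of SAEs, deaths, AEs leading to discontinuation, and Areas of Safety Interest will be provided as well".

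**The concern.** ABBV-3373 is adalimumab carrying a GRM payload, and the comparator is adalimumab without it. A grouped count of GC effects, compared between arms, is therefore the natural place to look for harm from the payload. The category that defines the group omits half of the GC toxicities that the protocol itself names in its rationale.

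Adrenal insufficiency is the omission that matters most. Under Section 4.1 the last ABBV-3373 dose is at Week 10 and subjects are followed to Week 24, which leaves 24 − 10 = 14 weeks in which a withdrawal effect could appear. Subjects who enter on low-dose GCs must also come off them by Week 4 in both arms (Section 5.4). Some adrenal events could thus arise without the payload, which makes a between-arm count of the grouped events more useful than isolated cases. If the list is followed literally, that count is not produced, and the GC row could look cleaner than the underlying data.

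**Working it through.** No design figure, rate or test enters this point. The check is a comparison of the sections.

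**Step 1. Match the six effects in Section 2.1 against the GC item in Section 6.1.**

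| Effect named in Section 2.1 | In the GC item of Section 6.1? | Where else the protocol treats it |
|---|---|---|
| HPA-axis suppression | No | Own management paragraph in Section 6.2; cortisol in Section 3.6 and Appendix J |
| Fracture due to osteoporosis | No | Eligibility criterion 16 (Section 5.1) |
| Hyperglycemia | Yes | Management paragraph in Section 6.2; criterion 16 |
| Glaucoma | No | Criterion 17 (Section 5.1) |
| Skin thinning | Yes, as skin atrophy | None needed here |
| Weight gain | Yes | None needed here |

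Result: 3 of 6 carried over, 3 of 6 absent. The Section 6.1 item has seven terms, so 7 − 3 = 4 of its terms (infections, cataract, hypertension, indigestion) are not in Section 2.1.

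**Step 2. See whether another AESI category catches the three.** The other seven categories are infections, malignancy, cardiovascular events, hematologic disorders, hepatic disorders, hypersensitivity and demyelinating disease. None covers adrenal insufficiency, fracture or glaucoma.

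**Step 3. See whether the GC item can be read as open.** It is introduced by *i.e.*, which defines. The cardiovascular item in the same list uses *e.g.*, which illustrates. Both forms occur in the section, so the plain reading of the GC item is a closed list. A slip is possible, but the text as it stands fixes the narrower category.

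**Step 4. Compare with Section 6.2.** Three of its management paragraphs concern effects that the protocol links to GCs: hypertension, hyperglycemia and adrenal insufficiency. The first two are in the GC item and the third is not. The paragraph itself ties the risk to the end of treatment: "can produce reversible HPA axis suppression with the potential for GC insufficiency after withdrawal of treatment".

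**Step 5. Trace what happens to an omitted event.**
- Collection: Section 6.1 collects all adverse events from first dosing until 70 days after study drug is discontinued, so the event is recorded.
- General tables: Section 7.4 tabulates treatment-emergent events by preferred term, by system organ class, by severity and by relationship, so the event appears there.
- Laboratory signal: Section 3.6 assesses cortisol change in both arms.
- Grouped GC summary: if the Section 7.4 summary follows the Section 6.1 list, the event is not counted.

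The loss is therefore confined to the grouped summary.

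**The case against.** The strongest reply is that nothing disappears. With 45 subjects, an adrenal, fracture or glaucoma event would be visible in the preferred-term tables, and HPA function is followed directly through cortisol. That is correct, and it limits the consequence. It does not answer the point, because a concept spread over several preferred terms is what a grouped category is meant to bring together, and cortisol is planned as a biomarker rather than a clinical event count.

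A second reply is that Section 2.1 is background on the drug class, is expressly non-exhaustive, and was never meant to define the AESIs; Section 6.1 has four terms that Section 2.1 lacks. This also has force, and it is why the mismatch is better called an inconsistency to reconcile than a flat contradiction. Section 6.2 is harder to set aside, since it concerns management in this trial.

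A third reply is that groupings are usually settled in the statistical analysis plan, and that Section 7.4 speaks of areas of safety interest without tying them to the Section 6.1 list. An analysis plan not shown here may use a wider search. But the point concerns a category that the protocol defines narrowly, not a detail that it leaves open.

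Four stronger readings are tempting and not supported:

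- A reader might infer that the events would be missed altogether. Collection and general tabulation rule that out.
- A reader might infer that the AESI summary is the trial's test of fewer GC side effects. With adalimumab as comparator, the trial cannot show fewer GC effects than a glucocorticoid, and Section 7.4 plans descriptive safety summaries.
- A reader might want to attach a probability of seeing an omitted event. The protocol gives no incidence for any of the three, and criteria 16 and 17 exclude subjects with prior osteoporotic fracture, high fracture risk or glaucoma, so any rate would be invented.
- A reader might object that counting infections as a GC effect blurs the category, as anti-TNF treatment causes them in both arms. Section 2.2 attributes serious infections to both classes, and serious and opportunistic infections already have their own AESI item, so showing infections separately is optional.

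**Conclusion.** The point holds in a limited form. As worded, the GC category in Section 6.1 excludes three of the six GRM-limiting effects named in Section 2.1, one of which has its own management paragraph in Section 6.2. A grouped GC summary that follows the list would not count them and could understate payload-related effects, chiefly adrenal insufficiency after ABBV-3373 stops.

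The size is modest: one incomplete grouping in a descriptive safety summary, with no effect on data collection, general event tables or efficacy inference. The conclusion assumes that *i.e.* is meant as written and that the Section 7.4 summary takes its content from the Section 6.1 list, which is the only such list in the protocol. If either assumption fails, the wording still needs correcting, but the reporting consequence shrinks.

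**What to change.** Reconcile Sections 2.1, 6.1 and 6.2 by adding three categories to the GC item in Section 6.1: adrenal insufficiency or HPA-axis suppression, fracture or osteoporosis, and glaucoma. In Section 7.4, state that the summary of areas of safety interest uses the Section 6.1 categories, so that these events are counted by arm. Changing *i.e.* to *e.g.* alone would remove the closed reading but would leave open whether the three are counted.

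The cost is a line of text and a slightly broader AESI grouping. The events are already collected as adverse events, so no visit, sample or procedure is added, and no dosing or management rule changes.
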